### 3.5 Handling of Missing Data and Outliers

## Statistical Analysis Plan (SAP) – Phase 3 Segment

---

No imputations will be conducted for missing data. No data will be excluded for being an outlier.

### 3.5.1 Missing data analysis methods

For the ITT analyses of efficacy, subjects with missing or unevaluable data regarding case definition will be considered cases (failures).

### 3.5.2 Missing or incomplete dates

#### 3.5.2.1 Imputation rules for missing or partial AE start/stop dates

- If the AE start date day is missing (month and year provided) then set the date to the first of the month, unless the month and year are the same as the first dose. In this case, set the date to the date of first dose.
- If the AE start month is missing (day and year provided) then set the month to January, unless the day and year are the same as the year of the first dose. In this case, set the date to the date of first dose.
- If the AE start date day and month are missing (year is provided) then set the month and day to January 1, unless the year is the same as the year of the first dose. In this case, set the date to the date of first dose.
- If the AE end date day is missing (month and year provided) then set the date to the last day of the month.
- If the AE end date month is missing (day and year provided) then set the date to the latest calendar month consistent with the day.
- If the AE end date month is missing (year is provided) then set the date to December 31.
- If the year of the AE start date or AE end date are missing, then a query to the site must be made to gather additional information.
  - If the start date is completely missing, then set the start date to the date of first dose. If the end date is completely missing, then set the end date to the date of latest follow-up.
  - If the start date day is missing (month provided), then set the date to the first of the month, unless the month is the same as the first dose. In this case, set the date to the date of first dose. If the end date day is missing (month provided), then set the date to the last day of the month.
  - If the start date month is missing (day provided), then set the month date to January, unless the day is the same as the first dose. In this case, set the date to the date of first dose. If the end date month is missing (day provided), then set the date to the latest calendar month consistent with the day.

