##### 6.2.1.1 Handling of missing or incomplete dates

###### Imputation rules for missing or partial adverse event start/stop dates

- If the AE start date day is missing (month and year provided) then set the date to the first of the month, unless the month and year are the same as the first dose. In this case, set the date to the date of first dose.
- If the AE start month is missing (day and year provided) then set the month to January, unless the day and year are the same as the year of the first dose. In this case, set the date to the date of first dose.
- If the AE start date day and month are missing (year is provided) then set the month and day to January 1, unless the year is the same as the year of the first dose. In this case, set the date to the date of first dose.
- If the AE end date day is missing (month and year provided) then set the date to the last day of the month.

- If the AE end date month is missing (day and year provided) then set the date to the latest calendar month consistent with the day.
- If the AE end date day and month is missing (year is provided) then set the date to December 31.
- If the year of the AE start date or AE end date are missing, then a query to the site must be made to gather additional information.
  - If the start date is completely missing, then set the start date to the date of first dose. If the end date is completely missing, then set the end date to the date of latest follow-up.
  - If the start date day is missing (month provided), then set the date to the first of the month, unless the month is the same as the first dose. In this case, set the date to the date of first dose. If the end date day is missing (month provided), then set the date to the last day of the month.
  - If the start date month is missing (day provided), then set the month date to January, unless the day is the same as the first dose. In this case, set the date to the date of first dose. If the end date month is missing (day provided), then set the date to the latest calendar month consistent with the day.
  - If the start date year is missing (day and month provided), then set the year to the year in which the patient was first screened, unless the day and month are the same as the first dose. In this case, set the date to the date of first dose. If the end date year is missing (day and month provided), then set the date to the latest calendar year in which the patient is followed.

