#### 3.8.2 Treatment Compliance

A full course of study product administration consists of 2 doses of vaccine. A summary by treatment group, as well as SARS-CoV-2 serostatus at baseline detailing the total number of doses received will be presented along with the reason a second dose was not administered or missed. A summary of subjects receiving the second dose outside the dosing window, 25 to 31 days post first dose, will be presented.

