#### 5.4.1 Adverse Events and Deaths

All AEs will be classified by Primary System Organ Class (SOC) and Preferred Term (PT) according to the Medical Dictionary for Regulatory Activities (MedDRA) Version 23.0 or higher.

In summaries by SOC and PT, AEs will be sorted by descending frequency within each SOC and PT according to the total number of events. In summaries by PT, AEs will be sorted by descending frequency according to the total number of events.

AEs will be classified as pre-treatment or treatment emergent (TEAE) defined as follows:

- Pre-treatment: any AE that started before the first dose date of the study treatment
- TEAE: Any AE that was newly developed at or after the first dose date of study treatment.

Details for imputing missing or partial start dates of AEs are described in SAP section [3.5.2.1](#).

AE summaries will include the following:

- All TEAEs
- Related TEAEs (AE will be defined as related if causality is either probably, possible, or definite)
- TEAEs by maximum severity, including grade  $\geq 3$
- Medically Attended AEs
- TEAEs leading to treatment discontinuation
- Serious TEAEs
- TEAEs leading to death

All AEs, including injection-site reactions, will be summarized among the Safety Population by frequency per treatment arm. These frequencies will be presented overall and separately by dose, and will depict overall, by system organ class and by preferred term, the percentage of subjects affected. In addition, an overall summary for categories above will be prepared by treatment arm.

Where a subject has the same AE, based on preferred terminology, reported multiple times in the treatment period, the subject will only be counted once at the preferred terminology level in AE frequency.

Where a subject has multiple AEs within the same system organ class in the treatment period, the subject will only be counted once at the system organ class level in AE frequency.

Adverse events by severity and separately by relationship will be summarized based on the most intense event during the treatment period and strongest relationship to study treatment, respectively.

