The main summary of safety data will be based on events occurring within 30 days of any dose. For this summary, the frequency of preferred term events will be compared between study arms with risk differences and 95% confidence intervals, using the method of Miettinen and Nurminen. As this analysis will use many event categories, and produce many confidence intervals, caution should be exercised when interpreting these confidence intervals. Separate summaries will be based on events occurring within 7 days of any dose and regardless of when they occurred.

The following sample SAS code will be used to construct confidence intervals of the risk difference with the method of Miettinen and Nurminen:

```
proc freq data = <DATASET>;
  tables armcd * <OUTCOME> / riskdiff(CL=(MN));
run;
```

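### The rule for a missing adverse-event start day ignores a recorded stop date, so an event that ended before Dose 1 can be counted as treatment-emergent; it also makes no provision for Dose 2

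*SAP*

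**What the plan says.** Phase 3 SAP section 3.5.2.1 gives the default for a start date with month and year but no day: "If the AE start date day is missing (month and year provided) then set the date to the first of the month". There is one exception: "unless the month and year are the same as the first dose. In this case, set the date to the date of first dose". Phase 2 SAP section 6.2.1.1 has the same rule. Neither section makes the start-date rules depend on a recorded stop date, and neither mentions the second dose.

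The AE analyses rely on this rule. In Phase 3 SAP section 5.4.1, straight after the pre-treatment and treatment-emergent definitions, the text reads: "Details for imputing missing or partial start dates of AEs are described in SAP section" 3.5.2.1. The treatment-emergent definition is "TEAE: Any AE that was newly developed at or after the first dose date of study treatment".

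Three kinds of output in that section depend on the start date:
- The main summary, which carries the between-arm risk differences: "The main summary of safety data will be based on events occurring within 30 days of any dose".
- Further summaries: "Separate summaries will be based on events occurring within 7 days of any dose and regardless of when they occurred".
- The frequency tables: "These frequencies will be presented overall and separately by dose".

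Phase 2 SAP section 7.7.1 plans the same outputs.

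**The concern.** An imputed date should not contradict a date that was actually recorded. Here it can. AEs are collected from consent, and screening may take place up to 30 days before Day 0 (Phase 3 SAP Appendix A, notes a and f; Phase 2 SAP Table 2, notes a and h). A pre-dose AE in the calendar month of Dose 1 is therefore quite possible. If its start day is missing, the exception moves it to the dosing date even when the stop date shows that it was already over. The result is a false treatment-emergent event, placed on the day that counts in every post-dose window.

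The second issue concerns attribution to a dose. The exception protects Dose 1 only, while the tables also report by dose and within 7 days of any dose. Dose 2 is planned 25 to 31 days after Dose 1, so it usually falls in a later calendar month. The first of that month then usually precedes Dose 2. A partly dated reaction to Dose 2 can be credited to Dose 1 or fall outside both 7-day windows.

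**Working it through.** The plan states no figure on this point, so there is none to reproduce. The check applies the written rule to dates.

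**1. Stop date before Dose 1**

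Inputs: the missing-day rule and its exception; the treatment-emergent definition; duration = end date − start date + 1 (Phase 2 SAP Table 3, Phase 3 SAP Table 2).

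Example: Dose 1 on 20 March, AE start recorded as March with no day, AE stop recorded as 12 March.
- Month and year match Dose 1, so the imputed start is 20 March.
- The start is on the first-dose date, so the event is treatment-emergent.
- The start is 0 days after Dose 1, so the event is inside the 7-day and the 30-day windows.
- Duration = 12 − 20 + 1 = −7 days.

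With a stop on 19 March, the day before dosing, duration = 19 − 20 + 1 = 0. Any stop date before Dose 1 in that month therefore gives zero or a negative number, and every such record is misclassified. The branch for a start date with only the year has the same first-dose exception and the same gap.

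**2. Onset soon after Dose 2**

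Inputs: the same rule, and the dosing window in Phase 3 SAP section 3.8.2: "A summary of subjects receiving the second dose outside the dosing window, 25 to 31 days post first dose, will be presented". Assumptions: Dose 1 dates spread evenly over a year; intervals of 25 to 31 days equally frequent; true onset 0 to 6 days after Dose 2; the start day missing; an event belongs to Dose 2 if its start is on or after the Dose 2 date.

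Example: Dose 1 on 10 March, Dose 2 on 7 April (28 days later), true onset 8 April, recorded as April with no day. The imputed start is 1 April, 22 days after Dose 1 and 6 days before Dose 2. That is outside both 7-day windows.

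Full enumeration: 365 × 7 × 7 = 17,885 combinations.

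| Result under the written rule | Count | Share |
|---|---|---|
| Imputed before Dose 2 | 15,533 | 86.8% |
| Outside 0–7 days of either dose | 11,756 | 65.7% |
| Outside 0–30 days of either dose | 0 | 0% |

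So 100 − 65.7 = 34.3% stay in a 7-day window. This happens mainly when Dose 1 fell in the last days of the previous month, when both doses share a month (about 8% of schedules, imputed to the Dose 1 date), or when onset runs into the month after Dose 2. No event becomes pre-treatment, because the imputed date is never before Dose 1.

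**3. Would a reset to the Dose 2 date be better?**

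The enumeration above contains only onsets after Dose 2, so it cannot show error in the other direction. As an illustration, assume onset uniform over the calendar month of Dose 2, with Dose 1 in an earlier month. Then 44% of onsets precede Dose 2, 25% fall 0 to 7 days after it and 31% fall later.

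| Misclassified | Written rule | Reset to Dose 2 date |
|---|---|---|
| 7-day status | 38% | 72% |
| Dose attribution | 52% | 44% |

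The reset puts every event inside the 7-day window, while only 100 − 72 = 28% truly belong within 7 days of either dose. Its attribution error is the 44% of onsets that precede Dose 2.

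**The case against.** The rule has a clear purpose. The cross-reference to it follows directly on the treatment-emergent definition, and anchoring to first dose is the cautious choice when nothing else is known. A known stop before dosing also arguably settles the matter under the pre-treatment definition, and a zero or negative duration would show up in data checks. That much is fair, but something else is known here: the stop date. The SAP sends partial start dates to the imputation rule with no override, so a program written to the plan produces the false event. Detecting it later would mean an unplanned correction.

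On Dose 2, most of the objection stands. A reader might infer that the safety comparison as a whole understates reactions to Dose 2. The documents do not support that. The 30-day main summary, the one with risk differences and confidence intervals, loses none of these events. Treatment-emergent status does not change, and the same rule applies in every arm. A reader might also infer that the error runs in one direction only, but that comes from enumerating only onsets after Dose 2. Nor do events always leave the 7-day table: about a third remain.

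Close follow-up should also keep undated early reactions uncommon. Phase 2 reviews diaries at the 7-day post-dose call. In Phase 3, diaries are used at selected sites only, so this reassurance is weaker there. Finally, neither SAP says that its by-dose tables assign events by imputed start date, so the attribution result rests on that assumption.

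**Conclusion.** The stop-date defect holds and is the main point. Any AE with a missing start day in the month of Dose 1 and a recorded stop before Dose 1 becomes a false treatment-emergent event, appears in the 7-day and main 30-day summaries, and has a duration of zero or less. This follows from the written rule without further assumption. The documents do not show that any such record exists, and the number is probably small.

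The Dose 2 gap is real but secondary. About 87% of the enumerated early post-Dose 2 onsets are imputed before Dose 2, and about 66% fall outside either 7-day window, given evenly spread dates and onset 0 to 6 days after Dose 2. The effect is confined to the by-dose and 7-day descriptive tables, for an unknown and probably small number of events. Whether a reset to the Dose 2 date would help depends on the true onset distribution, which the documents do not give. Under uniform onset it overstates Dose 2 and 7-day events; if reactions cluster just after dosing it would do better.

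Overall this is a minor point, worth correcting because the correction is so cheap.

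**What to change.** Add to Phase 2 SAP section 6.2.1.1 and Phase 3 SAP section 3.5.2.1, for all start-date branches:
- An imputed start date may not be later than the recorded stop date.
- An AE whose recorded stop date is before first dose is classified as pre-treatment.

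This takes two sentences in each SAP and a small change to the date-imputation program. It has no statistical cost, because it only prevents an imputed date from contradicting a recorded one.

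For Dose 2, leave the main rule as it is. State how the by-dose tables assign an event to a dose, and report how many AE start dates lack a day. If that number is not negligible, show a sensitivity version of the by-dose and 7-day tables only, in which a missing-day event in the month of Dose 2 (and not of Dose 1) is placed on the Dose 2 date. Note beside it that this version tends to overstate those counts. The cost is at most two extra tables.

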## Statistical Analysis Plan (SAP) – Phase 3 Segment

- If the start date year is missing (day and month provided), then set the year to the year in which the patient was first screened, unless the day and month are the same as the first dose. In this case, set the date to the date of first dose. If the end date year is missing (day and month provided), then set the date to the latest calendar year in which the patient is followed.

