## 2. Types of Planned Analyses

### 2.1 Data Safety Monitoring Board Analyses

The DSMB will meet approximately monthly until all subjects are enrolled in the trial, then bimonthly once all subjects are enrolled for the duration of the trial. The DSMB may also meet ad hoc as needed outside of the scheduled meetings and shall be disbanded upon completion of the trial.

The following data/documents will be generated for DSMB review:

- Baseline characteristics, demographics, participant disposition.
- Adverse events (AEs), adverse event of special interest (AESI), medically attended adverse events (MAAEs), and serious adverse events (SAEs).
  - Tabulated for each trial group by system organ class (SOC) and preferred term (PT), severity, seriousness, duration, treatment given, and the relationship to the trial drug and device.
  - Clinical test results and laboratory values (including raw values, changes from baseline, and clinical abnormalities).
- Listing of administration (injection) site reactions, including grading, duration, and treatment provided.
- Listing of deaths.
- COVID-19 disease.
- Any other supporting data requested by the DSMB.

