## Statistical Analysis Plan (SAP) – Phase 3 Segment

**Table 2: Derived Variables**

Variables	Formula
Demographic and Baseline Characteristics	
Body Mass Index	Weight (kg) / [height (m)] ^2
Derivation of Durations	
Study day at any visit	Date of interest – date of first dose of trial vaccine. One day is added if the difference is $\geq 0$ .
Duration of any events	End Date of Event – Start date of event + 1
Baseline Derivations	
Baseline	The baseline value is defined as the last observation prior to or on the date of the first dose of study drug; missing data will not be imputed.
Change from baseline	Post baseline value – Baseline; missing data will not be imputed.
Other Derivations	
Incidence	The number of subjects with a specific event divided by the total follow up time (in days) among the subjects in the treatment or control group and at risk of an initial occurrence of the event.
p	The true proportion of subjects with disease who receive INO-4800 relative to the total number of subjects with disease.
k	
The total amount of follow-up time (in days) in the placebo group divided by the total amount of follow-up time (in days) in the INO-4800 group
 
For calculating k, an individual subject's follow-up time is either:
 
 
the date of first disease diagnosis – date of the start of surveillance period + 1 (for subjects who are cases), or
 
the date of last follow-up – date of the start of surveillance period + 1 (for subjects who are non-cases).
 
 
The primary hypothesis of relative efficacy greater than 30% will be tested with <math>H_0: p \geq .70/(.70+k)</math> vs. <math>H_1: p < .70/(.70+k)</math>.

Vaccine Efficacy	1 – Risk in the vaccinated group / Risk in the unvaccinated group* 100, where risk is defined as the number of subjects with disease divided by the number of subjects in risk. Also equal to $(1-(1+k)p)/(1-p)$ , where k and p are defined above.
Confidence interval for efficacy	$[(1-(1+k)UBp)/(1-UBp), (1-(1+k)LBp)/(1-LBp)]$ , where UB and LB are the Clopper-Pearson upper and lower limits for the proportion, p; and p and k are defined above.
Geometric mean titer (GMT)	GMT is calculated as anti-log 10 (mean [log 10 Ti]) where Ti is the assay result for subject i.

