### 3.5.2.2 Imputation rules for missing or partial medication start/stop dates

- Start dates will not be imputed.
- Partial stop dates will be assumed to be the latest possible date consistent with the partial date. If day, month, and year are missing assign 'continuing' status to the stop date.

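### Partial AE end dates are imputed with no cap at last follow-up or death, so imputed events can end after the subject has left or died and AE durations are inflated

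*SAP*

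**What the plan says.** Phase 3 SAP 3.5.2.1 treats AE end dates according to what is missing:

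- Day missing: "If the AE end date day is missing (month and year provided) then set the date to the last day of the month".
- Month missing, day and year known: the latest month in which that day exists. December has 31 days, so this is always December.
- Year only: "If the AE end date month is missing (year is provided) then set the date to December 31". The Phase 2 wording is clearer: "If the AE end date day and month is missing (year is provided) then set the date to December 31". As worded, the Phase 3 rule overlaps the month-missing rule before it. I read it as the year-only rule.
- Year missing, day and month known: after a required query to the site, "then set the date to the latest calendar year in which the patient is followed".
- Nothing known: "If the end date is completely missing, then set the end date to the date of latest follow-up".

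Phase 2 SAP 6.2.1.1 has essentially the same rules. Neither SAP states a general cap elsewhere.

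Event duration is derived as "End Date of Event – Start date of event + 1" (Phase 3 Table 2; same formula in Phase 2 Table 3). Phase 3 section 2.1 lists duration among the items by which AEs are tabulated per group for the DSMB: "severity, seriousness, duration, treatment given". Phase 3 section 3.6 and Phase 2 section 7.1 include derived data in the subject listings.

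**The concern.** Only the completely missing end date is tied to the subject's actual follow-up. An end date with some information recorded can be carried past that point, and nothing in either SAP explains the difference. Followed exactly, the rules can produce an AE that ends after the subject died or left the trial, which is an impossible date in a listing. They can also turn a short event into one lasting many months in the SAPs' own duration variable. The overshoot tends to be larger for subjects who leave early in a calendar year. That is relevant to Phase 3, which was terminated and whose remaining analysis is restricted to primary efficacy and safety.

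**Working it through.** The documents give no figure on this point to reproduce, so I applied the Phase 3 rules literally to example dates. **All calendar dates below are assumptions for illustration.** Duration = end − start + 1 (Table 2). Overshoot = imputed end − last follow-up.

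| Case | True event | Last follow-up or death | What is recorded of the end | Imputed end | Overshoot (days) | Duration: true → imputed |
|---|---|---|---|---|---|---|
| A, year missing after query | 10–15 Dec 2021 | 29 Nov 2022 (Day 393 from Day 0 on 1 Nov 2021) | 15 Dec | 15 Dec 2022 | 16 | 6 → 371 |
| B, year only | 10–15 Feb 2022 | 1 Mar 2022 | 2022 | 31 Dec 2022 | 305 | 6 → 325 |
| C, month missing | 10–15 Feb 2022 | 1 Mar 2022 | 15th, 2022 | 15 Dec 2022 | 289 | 6 → 309 |
| D, day missing | 1–2 Mar 2022 | 3 Mar 2022 | Mar 2022 | 31 Mar 2022 | 28 | 2 → 31 |

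**Range of the overshoot** (non-leap year; the minimum is 0 in every case):

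- Day missing: exit on the 1st of a 31-day month gives 31 − 1 = 30 days.
- Month missing: an event ending in January on the day of exit is moved to the same day in December, 365 − 31 = 334 days.
- Year only: exit on 1 January gives 365 − 1 = 364 days.
- Year missing: the rule is bounded by the calendar year of follow-up, not the date. An end recorded as 31 December with last follow-up on 1 January also gives 364 days.

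**Effect of a cap alone**, end = min(imputed date, last follow-up or death): A 371 → 355, B 325 → 20, C 309 → 20, D 31 → 3. No end date then falls after exit, but case A hardly improves because the rule has already chosen the wrong year.

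**Effect of the year rule.** Taking the first year that puts the end on or after the start gives 15 Dec 2021 in case A, a duration of 6 days. Taking the latest year that fits under the cap would not be enough. With Day 0 on 20 Nov 2021, Day 393 is 18 Dec 2022. An AE from 10 Dec 2021 with end '14 Dec' would still be given 14 Dec 2022, a duration of 370 days, against 5 days under the first-year rule.

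**Which outputs use the end date.** Treatment-emergent status depends on the start date. The 30-day and 7-day summaries depend on when the event occurred. The AE summaries listed in Phase 3 section 5.4.1 and Phase 2 section 7.7.1 include none by duration. What remains is the derived duration, the Phase 3 DSMB tabulation and the listings.

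**The case against.** The strongest reply is that nothing of consequence uses the end date. No planned AE summary table is by duration, and section 2.1 does not say that imputed dates enter the DSMB displays. The Phase 3 SAP was finalised on 27 July 2022, after the version that recorded termination, so few DSMB reviews may have followed. The Phase 2 SAP names no display by AE duration. All of this stands, and it limits the point to a minor one. It does not make the rule right: the duration variable is defined in both SAPs, and derived data are to be listed.

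The missing-year rule applies only after a mandatory site query, so cases like A are a fallback. That also stands, but no such query is required for the year-only or month-missing rules.

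Imputing to the latest possible date is a deliberate convention, also used for medication stop dates without a stated cap. That explains the direction of the rule but does not justify dates after death or exit.

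A reader might go further in three ways that the documents do not support:

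- **That ongoing AEs are made to look resolved.** Medications have the rule "If day, month, and year are missing assign 'continuing' status to the stop date" and AEs have no counterpart. But the SAPs do not say that an AE recorded as ongoing counts as having a missing end date. That depends on a case report form field not shown here.
- **That a wholly unknown end date always comes out earlier than a partial one.** It does so only when the imputed date passes last follow-up. An AE with end 'Jan 2022' in a subject followed to June 2022 ends on 31 January, earlier than the completely-missing rule would give.
- **That the overshoot can be measured from the Phase 3 SAP's final date** (27 July to 31 December 2022, 157 days). A document version date is neither a follow-up date nor a trial-closure date.

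**Conclusion.** The point holds as a minor fault in both SAPs. Partial AE end dates have no cap at last follow-up or death, and the rules can give impossible end dates: up to 30 days late for a missing day, up to 334 for a missing month, and up to 364 when only the year is known or the year stays missing. Durations of many months come from the last three situations, not from a missing day. A short event whose end year stays unresolved after the query can be given a duration of about a year.

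It would be wrong to infer that safety or efficacy conclusions are biased, because no incidence, risk difference or efficacy result uses the AE end date. The number of affected records is not given, and the sizes above rest on assumed dates and a literal reading of the rules.

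**What to change.** Add to Phase 3 SAP 3.5.2.1 and Phase 2 SAP 6.2.1.1:

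1. Every imputed AE end date is the earliest of the date given by the rule, the date of latest follow-up and the date of death, and is never before AE start.
2. If the end year is still missing after the site query, use the first year that places the end date on or after AE start, subject to the same cap.

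While editing, align the Phase 3 year-only wording with Phase 2 so that it no longer overlaps the month-missing rule. If a SAP can no longer be amended, describe the change in the CSR, as both introductions require for deviations.

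The cost is one or two sentences per SAP and minor programming, with no new data. Two limits remain. Year-only end dates will still give long, conservative durations up to last follow-up: an AE from 10 March 2022 capped at an assumed 30 June 2022 lasts 113 days, against 297 uncapped. The first-year rule could shorten an event that truly lasted more than a year. With follow-up ending at Day 393, two years are both possible only if the earlier candidate end falls by about Day 28 (393 − 365), so this should be rare.
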